#### 3.3.3 Exclusion criteria

- 1. History of cholestatic chronic liver disease (e.g. primary biliary cholangitis, primary sclerosing cholangitis)
- 2. Trial participants without adequate treatment for HBV, HCV or NASH as per local guidance (e.g. antiviral therapy for chronic HBV or HCV infection or lifestyle modification in NASH)

<sup>1A woman is considered of child-bearing potential, i.e. fertile, following menarche and until becoming postmenopausal unless permanently sterile. Permanent sterilisation methods include hysterectomy, bilateral salpingectomy and bilateral oophorectomy. Tubal ligation is NOT a method of permanent sterilisation. A postmenopausal state is defined as no menses for 12 months without an alternative medical cause.

- 3. If received curative anti-viral therapy for HCV, SVR sustained for less than 1 years prior to screening
- 4. If receiving anti-viral therapy for HBV, less than 6 months on a stable dose prior to screening, with planned dose change during the trial or HBV DNA detectable
- 5. Weight change  $\geq$ 5% within 6 months prior screening in patients with NASH
- 6. Must take, or wishes to continue the intake of, restricted concomitant therapy (refer to Section 4.2.2.1) or any concomitant therapy considered likely (based on Investigator judgement) to interfere with the safe conduct of the trial
- 7. SBP <100 mmHg or DBP <70 mmHg at screening (Visit 1a)
- 8. Hepatic impairment defined as a Child-Turcotte-Pugh score  $\geq 8$  at screening
- 9. Model of End-stage Liver Disease (MELD) score of >15 at screening (Visit 1a), calculated by the central laboratory
- 10. ALT or AST >5 times upper limit of normal (ULN) at screening (Visit 1a), measured by the central laboratory
- 11. eGFR (CKD-EPI formula) < 20 mL/min/1.73 m^2 at screening (Visit 1a), measured by the central laboratory
- 12. Platelet count  $<50 \times 10^9/L$

**Boehringer Ingelheim** 

- 13. Alpha-fetoprotein >50 ng/mL (>50  $\mu$ g/L) at screening (Visit 1a), measured by the central laboratory
- 14. Prior orthotopic liver transplantation
- 15. Prior or planned TIPS or other porto-systemic bypass procedure during the trial conduct
- 16. Known portal vein thrombosis
- 17. History of clinically relevant orthostatic hypotension, fainting spells or blackouts due to hypotension or of unknown origin (based on Investigator judgement)
- 18. QTcF-interval >450 ms in men or >470 ms in women at screening (Visit 1a), a family history of long QT syndrome, or concomitant use of therapies with a known risk of Torsade de Pointes or planned initiation of such therapies during the trial (refer to Section 4.2.2.1)

Page 39 of 98

Proprietary confidential information © 2023 Boehringer Ingelheim International GmbH or one or more of its affiliated companies

- 19. Contraindication to any of the trial assessments (e.g. poor patient co-operation for HVPG,
- 20. Major surgery (major according to the investigator's assessment) performed within 12 weeks prior to randomisation (Visit 2) or planned during the trial, e.g. hip replacement.
- 21. Any documented active or suspected malignancy or history of malignancy within 5 years prior to screening (Visit 1a), except appropriately treated basal cell carcinoma of the skin or in situ carcinoma of uterine cervix
- 22. History of (in the 6 months prior to randomisation [Visit 2]), or ongoing, chronic drug abuse, or not expected to comply with the protocol requirements for any other reason that, based on Investigator judgement, makes the patient an unreliable trial recruit or unlikely to complete the trial as scheduled
- 23. Previous randomisation in this trial, previous exposure to BI 685509, or an allergy / contraindication to BI 685509 and matching placebo / or any of their excipients
- 24. Currently enrolled in another investigational device or drug trial, or less than 30 days or 5 half-lives (whichever is longer) prior to randomisation (Visit 2) since ending another investigational device or drug trial, or receiving other investigational treatment(s)
- 25. Women who are pregnant, nursing, or who plan to become pregnant while in the trial
- 26. Any other medical condition that, based on Investigator judgement, poses a safety risk for the patient or may interfere with the objectives of the trial

# **3.3.4** Discontinuation of trial participants from treatment or assessments

Trial participants may discontinue trial treatment or withdraw consent to trial participation as a whole ("withdrawal of consent") with very different implications; please see Sections 3.3.4.1 and 3.3.4.2.

However, if the trial participants agree, they should stay in the trial. Even if continued trial treatment is not possible, they should attend further trial visits to ensure their safety and to collect important trial data.

Measures to control the withdrawal rate include careful trial participant selection, appropriate explanation of the trial requirements and procedures prior to trial enrolment, as well as the explanation of the consequences of withdrawal.

The decision to discontinue trial treatment or withdraw consent to trial participation and the reason must be documented in the trial participant files and CRF. If applicable, consider the requirements for AE collection reporting (see Section 5.2.6.2).

Trial participants who discontinue after randomisation will not be replaced and may not be re-enrolled later. However, the Sponsor may decide to randomise more trial participants than originally planned, to account for a reduced sample size, if trial participants terminate early due to e.g. trial disruption (such as measures to control a global pandemic).

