# FLOW CHART

Trial Periods	Screening 		Randomise	d Treatment					Follow-Up
Visit	1a 	1b 	2 	3	4	5	6	EoT / ED 	EoS 
Week	-4		R	1	2	4	6	8	10
Day	-28		1	8	15	29	43	57	71
Time window for visits (days)	See footnot	te 1	N/A	$+_{2}$	+ 2	$+_{2}$	± 3	± 5	± 5
Fasting status 	NF	F	F	NF	NF	F	NF	F	F
Informed consent	х								
Register patient in IRT system via IRT call	Х								
Demographics 	х								
Medical history / baseline conditions 	х								
Concomitant therapy	х	Х	х	х	х	х	х	х	х
Anthropometric measures 	х		х	х	х	х	х	х	х
Vital signs 	х		x 	x 	x 	x 	х	х	x
Physical examination 	x 		(x)	(x)	(x)	(x)	(x)	х	(x)
Resting 12-lead ECG 	х		x 	x 	x 	x 	х	х	х
Safety laboratory sampling	х		х	х	х	х		х	х
Pregnancy testing 	Xs		Xu			Xu		Xu	Xu
Hepatic venous pressure gradient (HVPG) 		х						х	
Ultrasound (liver and spleen) 		Х				х		х	х
Review of in-/exclusion criteria	x	x	x						
Randomisation			x						

BI-VQD-12177\_40-106\_AD-03 (22.0)

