#### Footnotes:

- The screening period consists of 2 visits (Visits 1a/b). These visits should ideally be completed within a period of 4 weeks. There is no minimum duration. A trial participant can proceed from one visit to the next as soon as all results from the previous visit are available and if he / she remains eligible for the trial. Refer to Sections 5.1.2, 5.2.5.1, 5.2.5.2 and 6.2.1
- Visit 2 = enrolment / randomisation / Day 1 of trial medication. All assessments at this visit (excluding post-dose ECGs [refer to Sections 5.2.4, 6.2 and Appendix 10.1]) should be completed before the first dose of trial medication is administered
- 3. Trial participants who complete 8 weeks of treatment will have an End of Treatment (EoT) visit, followed 2 weeks later by an End of Study (EoS) visit. The last dose of trial medication will be administered in the evening of the day before the EoT visit. Trial participants who discontinue trial medication prematurely will have an Early Discontinuation (ED) visit completed instead of the planned treatment period visit. The ED visit should be performed within 7 days of discontinuing the trial medication, followed 2 weeks later by an EoS visit. Refer to Section 6.2.2.1 for details of assessments that should be performed during an ED visit and the EoS visit that follows it.
- 4. Fasting status: F = fasting (i.e. overnight fast, no food or drink, except water), NF = non-fasting
- 5. For further details refer to Section 6.2.1
- 6. Anthropometric measures = height (measured at Visit 1a only), weight, and waist and hip circumference. Refer to Section 5.2.1.1
- 7. Measurement of vital signs should precede the 12-lead ECG, and measurement of the 12-lead ECG should precede blood sampling and intake of trial medication at visits where a single ECG is required. The 12-lead ECG should be performed after the trial participant has rested for at least 5 minutes in a supine position. From Visit 2 onwards, the trial participants home BP monitoring equipment should be used in the clinic to measure vital signs (refer to Sections 5.2.2, 5.2.2.1 and 5.2.4)
- 8. At Visits 1a and at the EoT / ED visit, a complete physical examination is required. At all other marked visits, a physical examination is only required if the trial participant reports symptoms. Refer to Section 5.2.1

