#### 2.1.3 Secondary endpoints

Secondary endpoints include:

- occurrence of a response, which is defined as >10% reduction from baseline HVPG (measured in mmHg) after 8 weeks of treatment
- occurrence of further decompensation events (i.e. ascites, VH, and / or overt HE) during the 8-week treatment period
- occurrence of CTCAE grade 3 (or higher) hypotension or syncope based on Investigator judgement, during the 8-week treatment period
- occurrence of discontinuation due to hypotension or syncope during the 8-week treatment period

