- the trial participant has not successfully completed the dose titration period (i.e. Visit 4), but has persistent AEs or severe effects requiring down-titration of the trial medication (refer to Section 4.1.4.1)
- a female trial participant becomes pregnant. The trial participant will be followed up until birth or otherwise termination of the pregnancy. The data of the trial participant will be collected and reported in the Clinical Trial Report (CTR) until last trial participant last visit and any events thereafter will be reported in the BI Pharmacovigilance (PV) database (refer to Section 5.2.6.2.3)

Trial-specific procedures have also been defined for Investigators to follow in case of increased liver enzymes (AST, ALT, and total bilirubin) after randomisation. For details refer to Section 5.2.6.1.4 and Appendix 10.2 [P09-12413].

In the event of intolerance to BI 685509 after successful completion of the dose titration period at Visit 4 (e.g. persistent AEs despite two down-titrations, or severe effects at any dose), permanent treatment discontinuation should also be considered, based on Investigator judgement (refer to Section 4.1.4.1).

In addition to these criteria, the Investigator may discontinue trial participants at any time based on clinical judgement.

If a trial participant permanently discontinues the trial medication before the last allocated dose, an Early Discontinuation (ED) visit is required ideally within 7 days of discontinuing the medication. An EoS visit should be performed 2 weeks after the ED visit. Refer to Sections 6.2.2.1 and 6.2.3 for further details, including guidance with respect to trial assessments that should be included as part of an ED visit.

Boehringer Ingelheim will closely monitor and medically review all adverse events CTCAE Grade 3 and higher.

Boehringer Ingelheim will pause the enrollment of new patient in the trial and ensure the clinical data is reviewed by the data monitoring committee (DMC) for safety before proceeding with the trial if one of the following occurs:

- 1. more than two patients develop a CTCAE grade 3 or higher in the same category; OR
- 2. two or more patients meet the individual patient stopping criteria related to adverse event

In case of a temporary discontinuation, trial medication (BI 685509) should be restarted if medically justified; refer to Section 4.1.4 for details, including instructions regarding dose adjustments.

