4.1.5.2 Emergency unblinding and breaking the code

Emergency unblinding will be available to the Investigator via IRT. It must only be used in an emergency situation when the identity of the trial medication must be known to the Investigator in order to provide appropriate medical treatment or otherwise assure safety of trial participants. The reason for unblinding must be documented in the source documents and / or appropriate eCRF page. If a trial participant is unblinded by the Investigator, the trial participant has to be discontinued from the trial (refer to Section 3.3.4.1).

Due to the requirements to report Suspected Unexpected Serious Adverse Reactions (SUSARs), it may be necessary for a representative from BI's PV group to access the randomisation code for individual trial participants during trial conduct. The access to the

code will only be given to authorised PV representatives for processing in the PV database system and not be shared further.

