### 6.2.2.1 End of treatment / Early discontinuation visit

Patients who successfully complete the entire 8 week treatment period should have the assessments for the EoT visit performed as indicated in the Flow Chart. Such patients should be registered as completed in the IRT system. End of trial medication must also be recorded on the corresponding eCRF.

For patients who discontinue trial medication prematurely (for whatever reason), an ED visit (refer to the Flow Chart) should be completed instead of the planned treatment period visit (refer to Section 3.3.4.1). Ideally the ED visit should be performed within seven days of discontinuing the trial medication. The assessments performed at the ED visit should be in accordance with the Flow Chart, with the following exceptions:

- HVPG: not required
- •
- •
- biobanking sampling: not required

Patients who discontinue treatment early should be registered as discontinued in the IRT system. End of trial medication must also be recorded on the corresponding eCRF.

At the EoT and / or ED visit, patients should be reminded about restrictions (refer to Section 4.2.2) that still need to be observed up until the EoS visit (refer to Section 6.2.3). Home BP and HR monitoring should continue between the EoT / ED visit and the EoS visit.

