### 6.2.3 Follow-up period and trial completion

An EoS visit should be scheduled 2 weeks after an EoT and / or ED visit (refer to the Flow Chart and Section 3.3.4.1); participation in the trial is over once this visit has been completed; completion must be recorded on the corresponding eCRF.

When an EoS visit is performed after an ED visit, the assessments performed at the EoS visit should be in accordance with the Flow Chart, with the following exceptions:

For an individual patient, trial completion is defined as completion of the EoS visit within the specified time window and who has not discontinued trial medication prematurely. Following an EoS visit, the patient will return to standard medical care.

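### Participants who stop treatment before about Day 36–43 are not observed for the whole 8-week decompensation endpoint, although Protocol 3.3.4 asks them to keep attending visits

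*Protocol*

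**What the plan says.** **Staying in the trial.** Protocol 3.3.4 separates stopping treatment from withdrawing consent. Participants who stop treatment remain in the trial if they agree, and "they should attend further trial visits to ensure their safety and to collect important trial data". It states neither how many visits nor until when.

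**Visit rules.** Flow Chart footnote 3: "Trial participants who discontinue trial medication prematurely will have an Early Discontinuation (ED) visit completed instead of the planned treatment period visit". Section 6.2.2.1: "Ideally the ED visit should be performed within seven days of discontinuing the trial medication". Section 3.3.4.1: "An EoS visit should be performed 2 weeks after the ED visit". Section 6.2.3, on the EoS visit after either EoT or ED: "participation in the trial is over once this visit has been completed". Under 5.2.6.2.1 all AEs are collected up to EoS. After that there is no active monitoring; only new cancers and drug-related SAEs or AESIs that come to the investigator's notice are reported.

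**Endpoint and analysis.** Protocol 2.1.3 lists "occurrence of further decompensation events (i.e. ascites, VH, and / or overt HE) during the 8-week treatment period". Section 7.2.2 names premature discontinuation of trial medication as an intercurrent event, handles all such events by treatment policy, and ties that strategy to the Section 2.1 objectives. Section 7.2.4 presents the percentage of participants with an event. SAP 7.5.2.1 identifies decompensation from AE terms. SAP 7.8.1.1 ends the on-treatment period for AEs 7 days after the last intake and sends later AEs to follow-up listings.

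**Leaving treatment or leaving the trial.** Section 4.1.5.2: "If a trial participant is unblinded by the Investigator, the trial participant has to be discontinued from the trial". Section 5.2.4 speaks in the same way of participants who meet the ECG criteria. Both refer to 3.3.4.1, which lists these events as reasons to stop trial medication.

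**The concern.** A site that follows the visit rules closes out an early stopper at EoS, which can be weeks before Day 57. An endpoint defined over 8 weeks is then observed for a shorter and varying time, and the planned percentage makes no allowance for this: a participant last seen on Day 22 without an event counts the same as one followed to Day 57. Treatment policy asks what happened after randomisation whether or not treatment continued, so it needs data after stopping. Unlike HVPG, a decompensation event needs no invasive test, so it could be recorded without bringing the participant back for a procedure. At stake are missed late events in early stoppers and, if stopping differed between arms, the comparison of arms on this endpoint.

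**Working it through.** The plan gives no figure for follow-up after stopping. Its only computed figures, the probabilities in Protocol 7.5, do not bear on this point. The check is calendar arithmetic.

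**Inputs**
- Stop day *s*, counted from Day 1 (Visit 2).
- Delay from stopping to ED, *L* = 0 to 7 days (Flow Chart footnote 3; 6.2.2.1).
- ED to EoS = 14 days (3.3.4.1), with a window of ± 5 days in the Flow Chart.
- Planned end of the 8 weeks = Day 57 (Flow Chart), so 56 days from Day 1.

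**Formulas**
- Last observation = *s* + *L* + 14.
- Unobserved days = max(0, 57 − (*s* + *L* + 14)) = max(0, 43 − *s* − *L*).

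For *s* = 8: 43 − 8 − 7 = 28 and 43 − 8 − 0 = 35, so 28/56 = 50% to 35/56 = 62.5%.

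| Stop day | Last observation (nominal) | Unobserved days to Day 57 | Share of 56 days | Unobserved days with ± 5-day EoS window |
|---|---|---|---|---|
| 8 | Day 22–29 | 28–35 | 50–62.5% | 23–40 |
| 15 | Day 29–36 | 21–28 | 37.5–50% | 16–33 |
| 29 | Day 43–50 | 7–14 | 12.5–25% | 2–19 |
| 36 | Day 50–57 | 0–7 | 0–12.5% | 0–12 |
| 43 | Day 57–64 | 0 | 0% | 0–5 |

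**Where the gap closes.** It is zero once *s* ≥ 43 − *L*: Day 43 if ED falls on the day of stopping, Day 36 if it falls 7 days later. With the ± 5-day window these limits run from Day 31 to Day 48.

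**The nearer limit in the SAP.** Under the 7-day rule of SAP 7.8.1.1, AEs after a Day 8 stop are summarised only to Day 15, which is 57 − 15 = 42 days short of Day 57. Events between Day 15 and EoS are collected but go to listings. The SAP states no separate window for decompensation.

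**Effect on the arm comparison, illustration only.** The documents give no discontinuation or decompensation rate by arm, so every rate here is assumed: 8-week risk *r* of 5–20%, the same in both arms, with constant hazard *h* = −ln(1 − *r*)/56; 5% stopping on placebo and 10–30% on active; stops on Day 8, 15 or 29; ED on the day of stopping. A stopper is observed for *s* − 1 + 14 days.

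Most extreme case: *r* = 20%, 30% against 5% stopping, Day 8.
- *h* = 0.2231/56 = 0.00398. Observed time is 7 + 14 = 21 days. Observed risk in stoppers is 1 − exp(−21 × 0.00398) = 0.080.
- Active: 0.70 × 0.20 + 0.30 × 0.080 = 0.164. Placebo: 0.95 × 0.20 + 0.05 × 0.080 = 0.194. The shift is 3.0 percentage points in favour of active.
- Missed first events per 20 participants: 20 × (0.20 − 0.164) = 0.72 on active, and 0.12 on placebo.

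Over the whole grid with more stopping on active, the shift runs from about 0.1 to 3.0 points. With 5% stopping in both arms it is 0, although both percentages are still slightly low.

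**The case against.** **The sections may not conflict.** The ED and EoS visits are themselves further visits, and 3.3.4 refers to 3.3.4.1 for the detail. The amendment log also records the removal of an instruction on remaining visits and phone contacts as not applicable to this study. That is superseded text and no error, but it suggests that short follow-up may have been chosen. This softens the contradiction. It does not close the gap, because 2.1.3 and 7.2.2 still stand.

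**The treatment period may end with treatment.** Under 6.2.2 the period runs from Visit 2 to the EoT visit, so for a stopper one could take it to end early. The endpoint, however, names 8 weeks, and treatment policy does not end observation at the last dose.

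**Late events say little about the drug.** The half-life is about 9 to 15 hours (1.2.1) and the residual effect period 7 days, so observation for 14–21 days after stopping already covers two to three times that period. This stands for an on-treatment safety summary, which should be kept. It does not answer the treatment-policy question.

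**Stronger readings to avoid.** A reader might infer that early stops will fall mainly on active and that the drug will therefore look safer than it is. Dose-limiting orthostatic dysregulation (3.2) and the mandatory stop for persistent or severe effects during titration (4.1.4.1) make more stopping on active plausible. No rates are given, though, and in the earlier hepatic impairment trial orthostatic intolerance led to no discontinuation (1.2.3). The protocol also excludes participants with low blood pressure or a history of clinically relevant orthostatic hypotension. Nor do the documents establish that unblinded participants leave the trial altogether: 4.1.5.2 cites a section about stopping medication, so loose wording is equally possible.

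**Conclusion.** The concern holds as a follow-up gap with unclear wording; no bias in a known direction is shown. Observation ends nominally 14–21 days after stopping. Stops before about Day 36–43 therefore leave part of the endpoint window unobserved: about half or more of it for a Day 8 stop, and none from Day 43. Participants who stop because of a decompensation event are not affected, since their event is already recorded. The day counts rest only on the protocol's visit timings. Any shift between arms rests on unequal stopping, which is an assumption; within the assumed ranges it is at most 3.0 points and less than one missed event per 20 participants. The plan tests no hypothesis (7.1). SAP Section 4 records that the programme was discontinued, that no subject finished 8 weeks and that all subjects stop early, so the practical weight for this trial's results is small. The correction is still worthwhile because it is cheap and aligns the visit schedule with the protocol's own endpoint and strategy.

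**What to change.** 1. Reconcile 3.3.4 with 3.3.4.1, 6.2.2.1, 6.2.3 and the Flow Chart, and say exactly which contacts an early stopper has and when participation ends.
2. Keep the ED and EoS visits. For participants who agree and whose EoS would fall before the planned Week 8 date, add one telephone contact at that date to record decompensation events, hospitalisation and vital status, with participation ending after it.
3. State in Protocol 7.2.4 and 7.2.6 and in the SAP that the decompensation endpoint is counted to Day 57 regardless of treatment discontinuation, and keep the summary to last dose + 7 days beside it. Without this step the extra contact would feed only listings.
4. Reconcile the wording of 4.1.5.2 and 5.2.4 on leaving the trial with 3.3.4.1, which treats the same events as reasons to stop trial medication.

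Cost: protocol and SAP wording, and one call per early stopper. A participant who stops on Day 8 stays in the trial up to about 5 weeks longer (35 days); the extreme, a stop on Day 1 with ED the same day, is 57 − 15 = 42 days. No change to HVPG measurement or sample size is needed.
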